- p **Plasma and urine samples for JCV will be collected** at specified timepoints.
- q All participants will receive **prophylactic treatment** with 100 mg of methylprednisolone IV. In participants where methylprednisolone is contraindicated, equivalent doses of other IV steroids (e.g., dexamethasone) should be used as premedication. It is also recommended that participants receive an analgesic/antipyretic such as acetaminophen/paracetamol (1 g) and an IV or oral antihistamine, such as diphenhydramine 50 mg, 30–60 minutes prior to ocrelizumab or placebo infusions.
- r **Study drug administration:** The Treating Investigator must review the clinical and laboratory re-treatment criteria prior to re-dosing participants with study drug in all subsequent treatment cycles.

Table 3 Schedule of Activities: Safety Follow-Up

	Safety Follow-Up Period				Unscheduled Safety Follow-Up Visit ^g	End of Safety Follow-Up or Withdrawal from Study ^b
	Up to 48 Weeks After the Last Infusion: Visits Occur Every 12 weeks (± 7 Days) ^a					End of Observation
Assessment	12 Weeks Post-Final Treatment Visit ^c	24 Weeks Post-Final Treatment Visit ^d	36 Weeks Post-Final Treatment Visit ^e	48 Weeks Post-Final Treatment Visit ^f		
Routine safety laboratory tests ^h	x	x	x	x	x	x
FACS ⁱ	x	x	x	x		x
Urine pregnancy test ^j	x	x	x	x	x	x
HBV DNA ^k	x	x	x	x		x
Total Ig, IgA, IgG, IgM		x		x		x
HAHA ^l	x					
PK samples ^l	x					
Neurological examination	x	x	x	x	x	x
EDSS	x	x	x	x	x	x
Physical examination		x		x	x	x
Vital signs		x		x	x	x
Potential relapses recorded	x	x	x	x	x	x
ECG		x		x		x
Adverse events	x	x	x	x	x	x
Concomitant treatment	x	x	x	x	x	x
Telephone interview ^m	x	x	x	x		x
RCR (Protein) ⁿ		x		x		x

Table 3 Schedule of Activities: Safety Follow-Up (cont.)

	Safety Follow-Up Period				Unscheduled_Safety Follow-Up Visit ^g	End of Safety Follow-Up or Withdrawal from Study ^b
	Up to 48 Weeks After the Last Infusion: Visits Occur Every 12 weeks (± 7 Days) ^a					End of Observation
Assessment	12 Weeks Post-Final Treatment Visit ^c	24 Weeks Post-Final Treatment Visit ^d	36 Weeks Post-Final Treatment Visit ^e	48 Weeks Post-Final Treatment Visit ^f		
MRI ^o	----->				(x)	

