β-hCG = β human chorionic gonadotropin; CD = cluster of differentiation; DMT = disease-modifying treatment; EDSS = Expanded Disability Status Scale; FACS = fluorescence-activated cell sorting; HAHA = human anti-human antibody; HBcAb = hepatitis B core antibody; HBsAg = hepatitis B surface antigen; HBV = hepatitis B virus; MRI = magnetic resonance imaging; MS = multiple sclerosis; PCR = polymerase chain reaction; PK = pharmacokinetic; RCR = Roche Clinical Repository.

- ^a **Safety follow-up:** Safety follow-up will be carried out for 48 weeks starting from the date of last infusion of ocrelizumab. Visits will occur every 12 weeks. As this study will be closed on 31 December 2022, participants already in safety follow-up may complete this study period in the rollover Study MN43964. Safety follow-up applies to study participants who have completed the blinded treatment period (or open-label treatment period, if applicable) and to participants who withdraw early from treatment. *Participants who start treatment with commercial ocrelizumab or another DMT will discontinue from the study completely and will not enter or continue in the safety follow-up period. A Withdrawal from Study visit will be performed at the time of study closure for participants not rolling over to Study MN43964.*
- ^b **Withdrawal from Study Visit** for participants withdrawing from the study at any time.
- ^c **12-weeks post-final Treatment Visit:** only applies if a participant withdraws from treatment before the mid-cycle visit 12 weeks after the first infusion of the current treatment cycle.
- ^d **24-weeks post-final Treatment Visit:** only applies if a participant withdraws from treatment after the mid-cycle visit 12 weeks after the first infusion but before the end of cycle visit (24 weeks after the first infusion) of the current treatment cycle.
- ^e **36-weeks post-final Treatment Visit:** applies to study participants who have completed the blinded treatment period (or open-label treatment period, if applicable) and to participants who withdraw early from treatment.
- ^f **48-weeks post-final Treatment Visit/End of Safety follow-up:** applies to study participants who have completed the blinded treatment period (or open-label treatment period, if applicable) and to participants who withdraw early from treatment.

Table 3 Schedule of Activities: Safety Follow-Up (cont.)

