- ^g A dedicated (scheduled or unscheduled) safety follow-up visit directly prior to the start of an alternative MS treatment is required for participants who begin an alternative treatment for MS while in safety follow-up in order to assess the participant's clinical status and safety parameters (assessments to be performed as per schedule of activities (Table 3) depending on the study period in which the participant was in when the alternative treatment began).
- ^h **Routine safety laboratory tests:** Hematology, chemistry, and urinalysis. Samples collected during unscheduled visits should preferably be sent to and analyzed by the central laboratory unless results are required urgently.
- ⁱ **FACS including** CD19 and other circulating B cell subsets, T cells, natural killer cells and other leukocytes.
- ^j **Urine β -hCG [sensitivity of at least 25 mIU/mL]** must be performed in women of childbearing potential during safety follow-up while B cells remain depleted below normal levels. If positive confirm with a serum pregnancy test.
- ^k **Hepatitis monitoring:** If total HBcAb is positive at screening, HBV DNA measured by PCR must be negative to be eligible. For those participants enrolled with negative HBsAg and positive total HBcAb, HBV DNA (PCR) must be repeated every 12 weeks.
- ^l **HAHA and PK samples:** In any case of anaphylaxis, anaphylactoid reaction, or serious or severe hypersensitivity reaction, HAHA and ocrelizumab concentration samples should be collected as close as possible to the event and then at 4 and 16 weeks postdose.
- ^m A **structured telephone interview** will be done on a 4-week basis between visits *up to* 48 weeks after the last infusion to identify and collect information on any changes in the participant's health status that warrant an unscheduled visit (including new or worsening neurological symptoms that warrant an unscheduled visit).
- ⁿ **RCR (Protein)** 6 mL blood samples in EDTA tube for plasma will be taken from consenting participants for analysis of protein biomarkers.
- ^o MRI should only be performed for participants who begin an alternative treatment for MS, within the time window of 1 month prior to the start of an alternative MS treatment (unless MRI has already been performed within prior 8 weeks).

Table 4 Schedule of Activities: Open-Label Extension Phase

Cycle	OLE Phase ^{a, b}											Delayed Dosing Visit ^d	Unscheduled Visit ^e	Withdrawal from Treatment Visit
	1			2		3		4		N ^c				

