4.1.4 Safety Follow-Up Period

The safety follow-up period will begin when the participant completes or discontinues from the blinded treatment period or OLE phase for any reason. Participants should remain in the safety follow-up period for *up to* 48 weeks following the last infusion of study drug/open-label ocrelizumab (as applicable). During the safety follow-up period, participants will be assessed at clinical visits every 12 weeks. Telephone interviews will be performed every 4 weeks *between visits*.

Participants who start commercial ocrelizumab *or another DMT* will be discontinued from the study completely and will not enter or continue in the safety follow-up period.

Because this study will be closed on 31 December 2022, participants already in safety follow-up may complete this study period in the rollover Study MN43964.

It is important to distinguish between “withdrawal from treatment” and “withdrawal from study”. Participants who withdraw from treatment should be encouraged to remain in the study for the full duration of the safety follow-up period (*up to* 48 weeks from the last infusion).

Every effort should be made to ensure that participants who withdraw from study treatment complete the safety follow-up period and all related assessments, regardless of whether or not they receive alternative treatment for MS.

Table 5 Overview of the Study Design and Dosing Regimen

	Blinded Treatment Period											OLE Phase			
	5 Treatment Cycle (120 Wks) Minimum ^{a, b, c, d, h}											Variable ^{a, c, e, f, g, h}			
	1 st Cycle (Wks 0–24)		2 nd Cycle (Wks 24–48)		3 rd Cycle (Wks 48–72)		4 th Cycle (Wks 72–96)		5 th Cycle (Wks 96–120)		Additional Treatment Cycles ^{b, d} (Every 24 Wks)		Open-Label Treatment Cycle 1 ^{f, h}		Open-Label Treatment Cycles ^{b, c, ...N^{f, h}} (Every 24 Wks)
Randomization group	Day 1	Day 15	Wk 24	Wk 26	Wk 48	Wk 50	Wk 72	Wk 74	Wk 96	Wk 98	Wk 120 (Day 1)	Wk 120 (Day 15)	Open-label Day 1	Open-label Day 15	Open-label Day 1
A Ocrelizumab	Ocrelizumab 300 mg IV														
B Placebo	Placebo IV											Ocrelizumab 300 mg IV			

OLE=open-label extension; Wk=week(s).

^a Each treatment cycle has a duration of 24 weeks.

^b The blinded treatment period consists of a 120-week minimum period. Participants enrolled early in the study will undergo up to an estimated 2–3 additional treatment cycles, depending on the duration of enrollment and the total number of disability progression events.

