5.10.1.4 Visits During the Safety Follow-Up Period

Participants who discontinue treatment for any reason (including, but not limited to, withdrawal from blinded treatment, withdrawal from OLE phase, or Sponsor decision to terminate the study) will be followed up for *up to* 48 weeks after the last infusion in the safety follow-up period with visits every 12 weeks.

Participants should be encouraged to complete the safety follow-up period.

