5.13.1.1 Hepatitis Screening and Liver Function Monitoring

Participants with recurrent or chronic infection of hepatitis B or history/presence of hepatitis C must be excluded from enrollment into the study (see Section 5.3).

In addition, hepatitis B and C serology will be performed at screening. A positive result to either HBsAg or total HBcAb associated with positive viral DNA titers as measured by PCR, or a positive result for HepCAb should result in the participant’s exclusion. Participants with evidence of past resolved hepatitis B infection (i.e., positive total HBcAb associated with a negative viral DNA) can be enrolled, and will have the hepatitis B virus (HBV) DNA checked every 12 weeks. Participants in whom the viral DNA becomes positive but in whom the quantity is at the lower limit of detection of the assay should have the test repeated as soon as possible. Participants found to have a confirmed viral DNA positive test should be referred to a hepatologist for assessment immediately. These participants will not receive further infusions of ocrelizumab and will enter the safety follow-up period.

Liver function (i.e., ALT/SGPT, AST/SGOT, gamma glutamyl transferase [GGT], alkaline phosphatase, total bilirubin) should be reviewed throughout the study.

Participants developing evidence of liver dysfunction should be assessed for viral hepatitis and, if necessary, referred to a hepatologist or other appropriately qualified expert. Study drug should be withheld until the diagnosis of viral hepatitis has been excluded. Participants developing hepatitis B or C should be withdrawn from the study and should enter the safety follow-up period. Should treatment be prescribed, this will be recorded in the eCRF. Participants with viral hepatitis due to other agents, such as hepatitis A, may resume treatment after the participant’s recovery.

Information relating to the risk of recurrence of hepatitis B is provided in Section 7.3.1 and information relating to hepatitis B immunization is provided in Section 5.5.3.

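### Table 3 footnote d withholds the 24-week safety follow-up visit from participants who withdraw before mid-cycle, leaving a 24-week gap where the protocol requires a visit every 12 weeks

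*Protocol*

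**What the plan says.** The general rule appears in several places in the Protocol. The Table 3 header has "Visits Occur Every 12 weeks", with a ±7-day window, and footnote a has "Visits will occur every 12 weeks". Section 4.1.4 states: "During the safety follow-up period, participants will be assessed at clinical visits every 12 weeks". Section 5.10.1.4 covers anyone who discontinues treatment for any reason and follows them for up to 48 weeks "after the last infusion in the safety follow-up period with visits every 12 weeks".

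The footnotes to the four visit columns then say who attends each one:

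- Footnote c: the 12-week visit "only applies if a participant withdraws from treatment before the mid-cycle visit 12 weeks after the first infusion of the current treatment cycle".
- Footnote d: the 24-week visit "only applies if a participant withdraws from treatment after the mid-cycle visit 12 weeks after the first infusion", and before the end-of-cycle visit.
- Footnotes e and f: the 36- and 48-week visits apply to completers and to all early withdrawers.

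A separate rule covers participants enrolled HBsAg-negative and HBcAb-positive. Footnote k says "HBV DNA (PCR) must be repeated every 12 weeks", and Section 5.13.1.1 says these participants "will have the hepatitis B virus (HBV) DNA checked every 12 weeks".

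**The concern.** Footnotes c and d appear intended to avoid repeating visits already made on treatment. That works for completers and for those who leave late in a cycle. It fails for those who leave before mid-cycle: they have made neither the Week 12 nor the Week 24 cycle visit, yet footnote d gives them no 24-week follow-up visit.

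Sites therefore hold two conflicting schedules for this group. If they follow the footnotes, one scheduled set of safety laboratory tests, HBV DNA, B-cell counts and EDSS is skipped.

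The group is foreseeable. A Grade 4 infusion-related event requires withdrawal from treatment (Sections 5.6 and 6.2.2.1). Infusions fall on Day 1 and Day 15 in the blinded period and in the first extension cycle, and on Day 1 only after that (Sections 6.2.1.3 and 6.2.1.4). Withdrawals prompted by such an event will usually come before mid-cycle.

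These participants are also likely to be B-cell depleted at Week 24 if they received ocrelizumab. Section 7.3.1.1 reports a median time to repletion of 72 weeks (range 27 to 175) in the Phase II relapsing-remitting study. It also describes an apparent association between sustained immunoglobulin decrease and serious infection.

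**Working it through.** **Visits by group.** On-treatment visits are in weeks after the first infusion of the last cycle. Follow-up visits are in weeks after the last infusion.

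| Group | On-treatment visits in the last cycle | Follow-up visits under footnotes c to f | Longest nominal interval |
|---|---|---|---|
| Completers | 12, 24 | 36, 48 | 12 weeks |
| Withdraw after mid-cycle, before end of cycle | 12 | 24, 36, 48 | 12 weeks |
| Withdraw before mid-cycle | none | 12, 36, 48 | **24 weeks** |
| Withdraw before mid-cycle, footnote d reworded | none | 12, 24, 36, 48 | 12 weeks |

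The stated 12-week interval is reproduced for the first two groups but not for the third. The two clocks differ by 2 weeks when the second infusion was given, so the first interval after leaving the cycle is then 14 weeks for the first two groups (26 − 12, or 38 − 24). The gap in the third group is unaffected, because its Week 12 and Week 36 visits are both counted from the last infusion.

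**Length of the gap in days.**

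- As written: (36 − 12) × 7 = 168 days. With ±7 days at each end: 168 − 14 = 154 to 168 + 14 = 182.
- Under the rule: 12 × 7 = 84 days. With windows: 84 − 14 = 70 to 84 + 14 = 98.

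**What the skipped column holds.** Table 3 has 17 assessment rows apart from MRI. The 24-week column marks all but HAHA and PK: 17 − 2 = 15. Immunoglobulins, ECG, physical examination and vital signs are marked in neither the 12- nor the 36-week column, so for this group their next scheduled follow-up assessment is Week 48.

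**Interval for those four assessments.** They are also done at the Withdrawal from Treatment Visit (Tables 2 and 4). Let that visit fall w weeks after the first infusion of the cycle.

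- As written, Day 1 infusion only: 48 − w, with w = 0 to 12, gives 36 to 48 weeks.
- As written, both infusions: Week 48 falls 50 weeks after the first infusion; 50 − w, with w = 2 to 12, gives 38 to 48 weeks.
- With the 24-week visit kept: 24 − w = 12 to 24 weeks (or 26 − w = 14 to 24), then 48 − 24 = 24 weeks. The interval never exceeds 24 weeks.

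**Whether anything else fills Weeks 12 to 36.** The withdrawal visit does not, because in this group it falls before mid-cycle. The 4-weekly telephone interviews are not clinic visits. The unscheduled-visit column of Table 3 marks routine laboratory tests, EDSS, examinations and vital signs, but not HBV DNA, B-cell counts, immunoglobulins or ECG.

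**The case against.** The strongest reply is that this is a drafting slip that sites can resolve. The 12-week rule is stated without conditions in the synopsis, the Table 3 header, footnote a and two body sections, and Section 5.10.1.4 applies it to every discontinuation. That is very probably the intent. But footnote d is the more specific instruction and is worded as a restriction, whereas footnotes e and f show how a visit meant for everyone was written. A site that follows footnote d literally has not misread it.

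Several points reduce the consequence, and they stand:

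- The HBV DNA duty is separate and applies only to the HBcAb-positive subset. A site could honor it without a Week 24 visit, although the footnotes give no scheduled occasion for the sample.
- Blank cells in the unscheduled column mean not mandated. Table 2 footnote d and Section 5.10.1.5 let the investigator add tests. Those visits depend on symptoms or clinical need, so they soften the gap but do not replace a scheduled visit.
- The count of 15 overstates the loss. It includes the telephone interview, which continues anyway, and adverse-event reporting also continues. Pregnancy testing, HBV DNA and the repository sample apply only to subsets.
- A Week 24 B-cell count would mostly confirm depletion, given the reported range. The 72-week figure shows that participants are likely still depleted then; it does not show that this count would help time repletion.
- The study closes on 31 December 2022, and follow-up may be completed in the rollover study, so a change made now has limited reach.

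**Conclusion.** The concern holds. Read as written, footnotes c to f give participants who withdraw before mid-cycle visits at 12, 36 and 48 weeks, in conflict with the protocol's own 12-week rule and with 12-weekly HBV DNA testing. The loss is one of four follow-up visits per affected participant. The gap is twice the stated interval, and four safety assessments go 36 to 48 weeks without a scheduled repeat after the withdrawal visit.

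This rests on a literal reading of footnote d; a site that gave footnote a precedence would not produce the gap. How many participants fall in the group cannot be computed from the documents. Appendix 8 takes its follow-up schedule from Table 3, so the conflict carries into that substudy.

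This is a safety-monitoring matter. Sample size, power and type I error are unaffected. Initial progression must occur on treatment and the event is timed at onset, so any effect on confirmed progression is minor.

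**What to change.** Reword footnote d so that the 24-week visit applies to every participant who withdraws from treatment before the end-of-cycle visit of the current cycle (24 weeks after its first infusion), including those who withdraw before the mid-cycle visit. Footnotes c, e and f can stay. This restores visits at 12, 24, 36 and 48 weeks for early withdrawers and changes nothing for the other groups.

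The cost is one footnote edit and a clarification to sites. The visit already exists as a Table 3 column and adds no burden beyond the 12-week rule.

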2. BACKGROUND AND RATIONALE

2.1 BACKGROUND

2.1.1 Multiple Sclerosis

Multiple sclerosis (MS) is an inflammatory and degenerative demyelinating disease of the human CNS. It is a global disease that affects an estimated 1.3 million people worldwide, including approximately 630,000 in Europe and 520,000 in the Americas (International Federation of Multiple Sclerosis Societies 2009). The condition manifests as neurological deficits related to damage to the spinal cord, brainstem, optic nerves, cerebellum, and cerebrum. Resulting symptoms may include weakness, pain, visual loss, bowel/bladder dysfunction, and cognitive dysfunction. Diagnosis of MS typically occurs through the application of highly structured diagnostic criteria that rely on clinical observation, neurological examination, brain and spinal cord magnetic resonance imaging (MRI) scans, evoked potentials, and cerebrospinal fluid (CSF) studies (McDonald et al. 2001; Polman et al. 2005).

Multiple sclerosis is clinically subcategorized into 3 phenotypic disease patterns distinguished by the occurrence and timing of relapses relative to disease onset and disability progression (Lublin et al. 2014). These include relapsing-remitting MS (RRMS), primary progressive MS (PPMS) and secondary progressive MS (SPMS).

Primary progressive MS is a relatively rare form of MS, accounting for approximately 10%–15% of all people with MS. Primary progressive MS is characterized by a progressive course from disease onset without superimposed discrete clinical attacks or relapses (Ebers 2004, Miller and Leary 2007). Unlike RRMS, the typical age of onset for PPMS is older at approximately 40 years, and men are affected nearly as often as women (Cottrell et al. 1999). The absence of relapses imposes special challenges for diagnosis, requiring clinical evidence that the disease has advanced for at least 1 year from symptom onset (McDonald et al. 2001; Polman et al. 2005).

Natural history studies of patients with PPMS suggest a disabling course from symptom onset. In a well-characterized cohort of patients with PPMS from Ontario, Canada, the median time to the use of a unilateral cane or brace (Disability Status Scale 6 [DSS 6]) was 8 years and the median time to wheelchair use (DSS 7) was under 20 years (Cottrell et al. 1999). A higher proportion of patients with PPMS present initially with motor impairment, cerebellar ataxia and brainstem symptoms than patients with relapsing-onset, and spastic paraparesis is a common early clinical presentation (Andersson et al. 1999).

No treatment has been demonstrated to significantly slow the progression of disability in patients with PPMS, including therapies approved for the treatment of relapsing forms of

MS. A large Phase III randomized, controlled trial with glatiramer acetate (Wolinsky et al. 2007) and smaller randomized, controlled clinical trials evaluating mitoxantrone (Kita et al. 2004), interferon (IFN)- β -1a intramuscularly (IM; Leary et al. 2003), and IFN- β -1b (Montalban 2004) did not demonstrate a significant impact on clinical progression in the PPMS population. The most recently completed randomized, controlled PPMS clinical trial was the 439-participant Phase II/III Study U2786g (OLYMPUS), comparing rituximab with placebo over a 96-week treatment period. Overall, this study did not demonstrate a significant treatment effect. Subgroup analyses suggested that a younger, more active subset of participants with PPMS (defined by the presence of gadolinium [Gd]-enhancing lesions seen on MRI scans at baseline and higher lifetime rates of disability progression) may have benefitted clinically from anti-CD20 therapy (Hawker et al. 2009). Currently, PPMS remains a severely disabling condition with very high unmet medical need.

